Clinical trials identifier: **NCT03128658**

Principal Investigator: **[name]**

Protocol Title: **Trauma Induced Coagulopathy and Inflammation**

Date: **August 2, 2018**

Protocol Description: **This is a prospective observational trial designed to evaluate the factors that contribute to the development of trauma induced coagulopathy, post injury inflammation and the development of organ dysfunction in adult trauma patients. Demographic data, physiologic data, blood samples and clinical variables will be collected over the 5 days following traumatic injury.**

Protocol

Abstract

While a number of factors are known to be associated with the development of trauma induced coagulopathy (TIC), inflammation, and multi-organ failure, we currently cannot predict which patients are at risk for developing these life-threatening conditions with any certainty. In this prospective observational study, we will investigate the many factors that contribute to the development of trauma induced coagulopathy, post injury inflammation and the development of organ dysfunction in order to develop a multi scale computational algorithm and ex vivo models capable of clinical prediction. Using a convenience sample technique, demographic data, physiologic data, fresh and residual blood samples, urine samples, and clinical variables will be collected over 5 days following traumatic injury. In addition to a computational model, ex vivo models using microfluidic devices and high resolution cellular respirometry, and nucleic acid analysis will be used to predict the development of TIC and multi-organ failure.

Objectives

Overall objectives

1) Develop a computational algorithm to predict the development of trauma induced coagulopathy (TIC) 2) Validate ex-vivo microfluidic TIC models 3) Develop ex-vivo assays to predict the development of trauma-induced inflammation and the development of multi-organ failure

Primary outcome variable(s)

Coagulation parameters including thromboelastography and microfluidic assessment on admission, 3 hours, 6 hours, 12 hours, 24 hours, 48 hours, and 5 days post admission.

Secondary outcome variable(s)

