Respirometry of platelets, peripheral blood mononuclear cells, and neutrophils on admission, 3 hours, 6 hours, 12 hours, 24 hours, 48 hours, and 5 days post admission; Development of multiorgan failure within 30 days of admission; Level of free serum free nucleic acids; Expression of pro and anti-inflammatory proteins and genes and genetic variants in serum, platelets, and white blood cells.

Background

Traumatic injury results in 5-6 million deaths per year worldwide with \$518 billion global cost with about half of trauma deaths due to acute blood loss. Acute blood loss and standard resuscitation with crystalloids and stored blood products causes hypothermia, acidosis, tissue hypoxia, hypotension, inflammation, the activation and consumption of coagulation factors including platelets, the release of free nucleic acids, the development of mitochondrial dysfunction and eventually organ failure. Importantly, about a quarter of trauma patients display a coagulopathy, (trauma induced coagulopathy, TIC) which greatly increases the risk of death and/or the development of multiorgan failure. We currently, however, cannot predict who will develop TIC or its associated complications. In fact, two patients who have the same clinical presentation may have very different outcomes. Developing a multi scale computational model and ex-vivo point of care assays would allow us to efficiently identify and effectively treat at risk patients and potentially improve outcomes.

Study Design

Phase*

Not applicable

Design

Prospective, observational, convenience sampling of trauma patients 18 yrs old or older who present to the trauma bay will be included. Minimally injured patients will be compared to those with a systolic blood pressure of 90 mmHg or less, the need for blood product transfusion within 1 hour of admission, and/or an ISS of greater than or equal to 15. Demographic data including past medical/medication history as well as clinical data including continuous vital signs (when available) will be recorded. Blood samples (approximately 15 ml) and urine samples (approximately 10 ml) will be taken on admission, 3hr, 6hrs, 12hrs, 24 hrs, 48 hrs, and 5 days post admission. Residual blood samples (which would otherwise be discarded) will be obtained from the PPMC clinical laboratory on 0 and 2 days post admission. Blood samples may be analyzed for coagulation parameters included ex vivo microfluidic

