In addition to the PI's ([name] and [name]), this research will be conducted by the Penn Acute Research Collaboration (PARC) research coordinators and assistants. PARC provides 24 hour translational research services to the Penn Presbyterian community. All PARC research staff are CITI trained and will be familiar with the study protocol and execution prior to its initiation. The PI is a qualified trauma surgeon with clinical trial experience and training. The PARC research coordinators have clinical research experience and will directly oversee the training of research assistants in order to coordinate the study and ensure compliance. After each enrollment, the study coordinator will evaluate for study compliance. The entire research staff will conduct monthly meetings and the PI and research coordinator will meet at least every 2 weeks. All patients, including enrolled subjects, will be admitted to the trauma and surgical critical care service. They will be managed according to generally accepted medical standards for traumatic injury, which includes surgical interventions, damage control maneuvers, and sub-specialty consultation as needed and at the discretion of the treating trauma surgeon/surgical intensivist. Blood and urine samples will be processed and analyzed in the trauma at PPMC as well as at the PARC facility on 3 Mutch, PPMC. Blood and urine samples and case report forms will be stored at the PARC facility on 3 Mutch, PPMC.

Characteristics of the Study Population

Target population

trauma patients 18 years or older who present to the trauma bay

Subjects enrolled by Penn Researchers

300

Subjects enrolled by Collaborating Researchers

0

Accrual

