This will be prospective observational study using convenience enrollment. Injured patients who present to the trauma bay will be evaluated by the on call trauma surgeon and as well as the PARC research assistant. If eligibility criteria are met, the research blood samples will be drawn at the same time as routine clinical samples. Depending on the research expertise available (e.g. microfluidic assessments or cellular respiration experiments), eligible patients may not have all the research variables investigated at each time point. Given that we will be recruiting a number of minimally injured patients, as well as injured patients with significant variability (eg severity of injury, age, gender, race, and past medical history), a large accrual number is required in order to develop a computational model that can accurately determine which factors predict the development of TIC, inflammation and

multiorgan failure.

Key inclusion criteria

In order to develop a robust predictive model, we will need to include a variety of injured patients ranging from minimally injured to severely injured. Inclusion criteria, therefore, will include any trauma alert activation. This highest level of activation is reserved for patients who meet either physiologic parameters (e.g. hypotension) or who have a mechanism of injury that would suggest significant injury (e.g. high speed motor vehicle crash). that being said roughly 30% of trauma alerts are not found to have significant injury. Only patient's whose age is equal to or greater than 18 years old will be included.

Key exclusion criteria

Transfer to trauma service of greater than 6 hours Known pregnancy - these patients are excluded because drawing multiple blood samples has an unknown risk to the fetus. Women of child bearing age, however, will be eligible. If they are found to be pregnant before enrollment, they will be excluded (eg. obvious gravid uterus, + fetus seen on trauma ultrasound, or + pregnancy test, which is routinely done on all female trauma patients) . If they are found to be pregnant after the initial blood draw, this sample will be processed, but no additional blood samples will be taken. The patient, or next of kin if appropriate, will be asked to consent for analysis of the processed sample and for continued clinical data collection.

Vulnerable

Populations

Children Form

Pregnant women (if the study procedures may affect the condition of the pregnant woman or fetus) Form

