Patients who develop coagulopathy, altered cellular respiration, or multi-organ failure will be compared using T-tests or Mann-Whitney tests for continuous variables and Chi-squared or Fischers exact tests for dichotomous variables. Spearman's rank correlation will be used to assess associations between continuous variables. Logistic regression analysis will be used to identify risk factors for the development of trauma induced coagulopathy or multiorgan failure.. Receiver operating characteristic curves will be used to assess accuracy of microfluidic measurements compared to standard measures of coagulation . Continuous deidentified data including vital signs, laboratory values, and medications will be shared with collaborators at Princeton University in order to create a mathematical model. The computational whole-patient systems model is a multiscale, multi-compartment model whose state-space is defined by a very large and heterogeneous set of variables as well as a large number of input parameters. It is straightforward to make direct contact with the clinical trauma blood profiles because the measured variables in these profiles are also included in the model state space. This comparison first will be used to establish the validity of the model. Here, the model will simply be integrated in time for various initial trauma conditions in an attempt to determine whether the model can be predictive. In particular, we will determine whether it is possible to reproduce the variation between the various time states at admission,3, 6, 12, 24, 48 hours and 5 days post admission. A more challenging data mining application is to discover new variables that are more predictive of clinical outcomes than those employed in current clinical protocols. The workhorse data mining technique we plan to explore, extend, and use to establish links between our multiscale model and clinical data is known as Diffusion Maps. This is a framework based upon diffusion processes for finding meaningful geometric descriptions of data sets, even when the underlying geometry of the data is complex, nonlinear and corrupted by noise. The method is based on the construction of a Markov transition probability matrix corresponding to a random walk on a graph whose vertices are the data points with transition probabilities being the local similarities between pairs of data points. The framework relates the spectral properties of Markov processes to their geometric counterparts and it unifies ideas arising in a variety of contexts such as nonlinear dimensionality reduction methods, machine learning, and harmonic analysis. The first few eigenvectors of the sparse Markov matrix are then used to generate a new set of intelligent coordinates that embody the intrinsic geometry of the data set. These are the diffusion map coordinates. Most importantly, these eigenvectors integrate the local similarities into a globally efficient low-dimensional representation of the complex geometric structure. The usage of eigenvectors of similarity matrices for dimensionality reduction is not new. In fact, the classical method of principal component analysis (PCA) computes principal components as eigenvectors of the covariance matrix of the data set and find a low dimensional representation of the data by projecting it onto the subspace spanned by the first few principal components that capture the most variability (or energy) of the data. Diffusion Maps is a successful generalization of PCA to complex nonlinear data sets whose structure is unknown in advance: unlike PCA, the diffusion map coordinates are nonlinear projections of the data; moreover, the nonlinear embedding is based only upon local similarities of neighboring data points. Diffusion Maps first will be used on the multiscale simulation data sets. This will establish macroscopic observables that define the trajectory of the overall patient-scale model. This is crucial because it is much simpler to establish a connection to patient outcome when only a few variables are being tracked (instead of the large variable space that defines the full multiscale model). However, these variables are generally not obviously connected to clinical variables and we will use the simulation data to establish relationships between the Diffusion Maps variables and actual measureable quantities. The result of this work will be to isolate variables that are highly predictive of patient outcome and allow assessment of different interventions.

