There are no direct benefits to study participants. The benefit will be toward advancing our knowledge of how severely injured patients develop complications such as coagulopathy and organ failure. This study will hopefully help us develop better assays to identify and treat patients at risk.

Alternatives to Participation (optional)

None. If a subject chooses not to participate he/she will receive standard care.

Data and Safety Monitoring

After each enrollment, the PARC research coordinator will audit the case report form in order to ensure proper consent procedures were performed, that data collection and entry are accurate and that personal data is stored properly. Data analysis will be performed after every 50th subject enrolled.

The following documents are currently attached to this item:

There are no documents attached for this item.

Risk / Benefit Assessment

This study presents minimal risk to patients.

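### Does analysing the data after every 50th of 300 subjects inflate the false-positive rate?

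*Combined protocol and SAP*

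**What the plan says.** The schedule is a single sentence under Data and Safety Monitoring: "Data analysis will be performed after every 50th subject enrolled". It follows a sentence that has the research coordinator audit the case report form after each enrolment. Planned enrolment, under "Subjects enrolled by Penn Researchers", is 300, with none from collaborators. The protocol does not state six analyses; the number follows by division.

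The Analysis Plan lists methods for the study as a whole. Groups "will be compared using T-tests or Mann-Whitney tests for continuous variables and Chi-squared or Fischers exact tests for dichotomous variables", and the plan adds Spearman correlation, logistic regression, ROC curves and computational modelling with Diffusion Maps. None of these is tied to a 50-subject analysis. No section gives a significance level, a multiplicity rule or a stopping rule, or names a final analysis.

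The primary outcome is a set of measurements: "Coagulation parameters including thromboelastography and microfluidic assessment on admission, 3 hours, 6 hours, 12 hours, 24 hours, 48 hours, and 5 days post admission". The sample size is justified only in words, under Accrual: "a large accrual number is required in order to develop a computational model". The same section warns that eligible patients "may not have all the research variables investigated at each time point".

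**The concern.** Testing the same hypothesis repeatedly on accumulating data, with no adjustment, raises the chance of at least one false positive. Here the sentence says data analysis, and the only analyses the protocol defines include significance tests. Nothing forbids running those tests at 50, 100, 150 and so on and reporting whatever crosses the line.

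Early hits would also be the least reliable. The Background says that "about a quarter of trauma patients display a coagulopathy", so the first analysis would hold only 12 or 13 patients with trauma-induced coagulopathy (TIC), and only a large observed difference could reach significance. The study exists to find predictors of coagulopathy and organ failure, so false predictors would damage its main product. A related worry is that seven time points, tested separately and without adjustment, add false positives even at a single analysis.

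**Working it through.** **Inputs.** From the protocol: 300 subjects, an analysis every 50, seven time points, and TIC in about 25%. Assumed because not given: two-sided 5% tests (range 1% to 10%), TIC range 15% to 35%, correlation between time points 0.3 to 0.7. The protocol has no alpha, power or effect size, so there is no sample-size figure to reproduce.

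**1. Number of analyses.** 300 / 50 = 6, including the one at full enrolment.

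**2. One null association read at every analysis.** With equal increments, Z at analysis k is the sum of k independent standard normal increments divided by √k. Numerical integration of the joint distribution with |Z| > 1.96 gives the cumulative chance of at least one crossing:

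| Subjects | 50 | 100 | 150 | 200 | 250 | 300 |
|---|---|---|---|---|---|---|
| Chance | 0.050 | 0.083 | 0.107 | 0.126 | 0.142 | 0.155 |

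Simulation agrees (0.154 to 0.155). At an assumed level of 1% the six-look figure is 0.036; at 10% it is 0.281.

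**3. The same association read only at 300.** The chance is 0.050, whatever was computed earlier, provided the test itself was not chosen from interim results.

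**4. What happens to early hits.**
- First significant at 300: 0.1548 − 0.1417 = 0.0131.
- Significant at 300 and also earlier: 0.0500 − 0.0131 = 0.0369.
- Share of early hits that persist: 0.0369 / 0.1417 = 26%. About 74% are therefore gone at 300.
- Share of all chance hits first seen at 50: 0.050 / 0.1548 = 32%. By 100: 0.0831 / 0.1548 = 54%.

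**5. Size of difference needed.** The smallest significant observed difference, in SD units, is 1.96 × √(1/a + 1/b), with a the TIC cases and b the rest.
- At 50: a = 50 × 0.25 = 12.5, b = 37.5, giving 0.64 SD (0.78 at 15% TIC, 0.58 at 35%).
- At 300: a = 75, b = 225, giving 0.26 SD (0.32 to 0.24).

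**6. Seven time points at one analysis.** If seven separate null tests were run, the chance of at least one false positive would be 1 − 0.95⁷ = 0.302 under independence, and 0.27, 0.23 and 0.18 at correlations 0.3, 0.5 and 0.7. The Analysis Plan does not say such tests will be run. It mentions the time points only when asking whether the computational model reproduces the variation between them.

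**7. Cost of compulsory Benjamini-Hochberg control.** Power for a real effect that has 80% unadjusted power, by simulation at correlations 0.3 to 0.7 (family sizes assumed; 35 and 70 correspond to five and ten measures at seven times):

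| Tests | Real effects | Power |
|---|---|---|
| 7 | 1 | about 55% |
| 7 | 3 | about 65% |
| 35 | 1 | about 35% |
| 70 | 1 | about 28% |
| 70 | 7 | about 41% |

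**The case for a change.** The best argument for changing the plan is that the benign reading is not secure. Auditing for accuracy is already assigned to the coordinator after each enrolment, so the every-50 activity is something else, and it is called data analysis. The tests in the Analysis Plan are never excluded from it. The primary outcome names no single parameter or time, which leaves wide choice over what to report and when. A sentence naming the final analysis would cost almost nothing.

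Part of this stands. The wording is thin, and the arithmetic above is right on its own condition. There is also a subtler point: the 300-subject data contain all the interim data. If predictors or cut-offs were picked because they looked good at 100, the final test of those same choices would no longer hold its nominal level. Analyses are also triggered by enrolment, while multiorgan failure is followed for up to 30 days (Procedures), so a final analysis has to wait for the last subject's follow-up.

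These are matters of ordinary analytical conduct, and the plan as written does not require anyone to do otherwise. The 15.5% needs three things together: the same test at each analysis, a 5% reading each time, and any hit reportable. The protocol states none of them. No enrolment, treatment or stopping decision depends on an interim result, so a group-sequential boundary would protect nothing. The one place that mentions giving out results (Additional Information to Subjects) puts this at the study's conclusion. That fits a single final report, although it does not prove one.

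**Conclusion.** No change follows. The missing purpose for the every-50 analyses is a gap in detail that a competent analyst fills by using them to check completeness, assay performance and model building, and by reporting associations once, from the complete data. On that reading the error for one association whose test was not selected on interim data is 5%. The alternative figure of about 15.5% (3.6% to 28.1% for assumed levels of 1% to 10%) belongs to a practice the protocol does not describe.

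The study sets out to develop models and assays and states no confirmatory hypothesis or error rate, so no declared error rate is breached. Adjusting across time points and biomarkers is a fair trade-off to leave open. Over seven tests it lowers the chance of any false positive to about 4% to 5%, but over the larger number of measurements this protocol collects it could cut power from 80% to roughly 28% to 41%. Readers of the eventual report should treat the associations as exploratory. The conclusion would differ if an interim result were used to stop enrolment or were published as a finding in its own right; nothing in the documents provides for either.
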